10.0 Recruitment Methods

The Project Coordinator will oversee all study recruitment and enrollment activities. Participants will be recruited through recruitment materials (e.g., flyers, letters, and handouts/postcards), the Buffalo Research Registry, and web-based recruitment (e.g., departmental website, Facebook, Twitter, Craigslist, ResearchMatch, ClinicalTrials) disseminated through the local community, university campuses, and medical clinics including UB-MD, the university physician network, Urban Family Practice, and the Upstate New York Practice Based Research Network which is engaged in multiple research projects to improve patient care in Western New York.

We may also use the i2b2 database through UB's Institute for Healthcare Informatics (IHI) to recruit participants from the UBMD medical data base

The study team may also utilize the University at Buffalo's Clinical and Translational Science Institute (CTSI) for recruitment assistance and consultation. The CTSI's Recruitment Team provides resources, guidance on appropriate recruitment strategies, and assistance in linking out study team with partners to effectively reach recruitment goals and target populations. We may also work with CTSI Community Engagement Team (CET) to create awareness of the study through their professional and community contacts. The tools they have available may include the Buffalo Research Registry (BRR), the Patients Voices Network (PVN), the Conventus CTSI/PVN Research Table, and conducting outreach at various community events. The BRR is a voluntary registry which can connect us to community members who have completed a health profile and are interested in participating in research. These community members have agreed to be contacted about potential research opportunities based on their self-reported information. These tools are method by which the CET distributes IRB-approved recruitment information to community members.

The CET also tables at many events in the community throughout the year and may display the IRB approved flyer for this project at their table at community events. Examples of events the CET attends include Good for the Neighborhood hosted by Independent Health Foundation, UB on the Green, Juneteenth, Elmwood Arts Festival and many others.

The CET also hosts a standing table at the Conventus Building on the 4th floor of UBMD where the IRB approved flyer can be made available to community members and patients. This will occur only after agreement between the CRL and UBMD Conventus partners that the study is appropriate for the Conventus space.

Additionally, a database of participants that have been involved in previous studies at the University at Buffalo Behavioral Medicine laboratory that expressed interest in future studies will be used. Participants who have indicated interest in contact for future studies will be contacted by email or phone with the study advertisement and survey link.

In addition, several other IRB-approved projects in our lab are recruiting participants who are also pre-diabetic. To minimize the likelihood participants screen for multiple projects in our lab, and in order to efficiently direct participants to the study that might suit them, a shared online (Qualtrics) questionnaire will be used that asks participants questions about their height and weight, diabetes/prediabetes status, if they are taking medications for blood glucose management, hypertension, or high cholesterol, if they are interested in weight loss, if they shop at local grocery stores, and if they are on public assistance.

11.0 Procedures Involved

Upon arrival to the Division of Behavioral Medicine ([name]), participants will be greeted and escorted to a private interview room where they will be given a verbal explanation about the study and provide documented consent. After signing the consent forms, participants will have their blood HbA1c, blood pressure, cholesterol, height and weight measured to calculate BMI, complete measures of delay discounting and study questionnaires including demographics, consumption, alcohol, tobacco, substance use, and executive function such as time perspective and memory. In addition, participants may sign forms for release of their relevant medical records to confirm their eligibility (e.g., diagnosis with prediabetes). Participants will be given a choice as to whether they would like their screening results shared with them and/or with their physician. If participants have values at a certain critical level (e.g. critically high blood pressure) they may be automatically notified. Participants may also complete a urine drug screen to confirm non-substance abuse and female participants may complete a urine pregnancy test to ensure eligibility. If throughout the study there is reason to believe a participant has become pregnant (i.e. the participant expresses that is their belief), we will provide pregnancy testing. If the pregnancy results are positive, the participant will be informed and they will not be eligible to continue with the study. Following the screening session, participants will be reviewed by members of the study team to make a decision if the participant is eligible.

Participants will also be given a choice as to whether they would like to be re-contacted after the conclusion of their 6-month involvement in study treatment in order to complete in a longer-term follow-up assessment that would occur at about 6 months after study completion, or at about 12 months after their initial

baseline session and would be conducted virtually via video conference.

Participants will be informed that their decision about being re-contacted for the longer-term follow-up will in no way preclude them from being involved in the study over the initial 6-month period.

If participants are determined to be eligible (e.g., have an HbA1c measurement in the prediabetes range, are not pregnant, do not report alcohol or substance misuse, are able to adhere to all study procedures, etc.) they will be followed up by phone call or email (or preferred method of contact) within one week and scheduled for a baseline appointment. They will also be given a detailed orientation of what will be expected of them during the study, including tasks they need to complete, recording food consumption and activity levels, and frequency of visits to our lab. At the baseline assessment session, eligible participants may also be provided with an Actigraph WGT3X-BT accelerometer to measure physical activity. They will be instructed how to properly wear the accelerometer and asked to record a diary of its wear-time. After wearing the accelerometer for about 7 days, participants may be asked to visit the lab to return it. At the baseline session participants will also be instructed on how to complete a food recall, complete measures of delay discounting, behavioral economic demand, demographics, working memory, medication adherence, and physiological measures (e.g. HbA1c, cholesterol, weight, etc).

After the first several weeks of treatment (about 6 weeks), eligible participants will be randomized to one of two groups, BT-EFT or BT. Participants in both groups will first attend weekly group meetings followed by bi-weekly group meetings, and then monthly group meetings for up to 6 months. Group sessions may be audio or video recorded so that if a participant misses the meeting, they are able to receive the information and learn the materials on their own time. They will be provided general information on healthy diet, physical activity and medication adherence. During the in lab appointments participants will be taught a number of behavioral treatment techniques. The treatment includes: 1) The Traffic Light Diet, which utilizes RED, YELLOW, and GREEN labels for food to guide participants toward the goal of consuming low energy dense, low glycemic, high nutrient dense foods; 2) the Traffic Light Activity Program, which also utilizes RED, YELLOW and GREEN labels for different levels of caloric expenditure, and 3) a variety of behavioral techniques, including stimulus control, self-monitoring, goal setting, problem solving, resetting rewarding mechanisms by reducing need for immediate gratification, finding behavioral substitutes for highly reinforcing food, and EFT (for the intervention group).

During each treatment meeting, participants will be weighed and then have a group session that lasts up to 60 minutes either preceded or followed by a session with a case manager that may last up to 30 minutes. The group sessions review information about weight loss and maintenance and engage in group problem solving for participants who are struggling with behavior change. During the individual meeting with their case manager, participants are taught behavior change techniques and review and address diet and activity self-monitoring and any barriers to adherence with the weight-loss behaviors.

After participants are randomized, participants in the EFT group will be asked to generate episodic cues similar to the tasks used in our previous studies on EFT's effect (Daniel et al., 2013). Each group will list and describe events for different time periods. The episodic component of the thinking task will occur while the participants are asked to describe what they are imagining about each event (e.g., vacations, weddings, parties, and so forth). EFT participants will list positive future events they are looking forward to and list events that could happen at different general future time points (e.g., 1 month, 2-6 months, 7-12 months). In contrast, the BT group will not generate any cues. All EFT participants may rate the salience, valence, arousal, feasibility and vividness of each event and events with the highest ratings for vividness will be used in the generation of episodic cues. An "imagery" score may be calculated by averaging the frequency/vividness scores for each event. Reductions in rate of discounting occur at higher levels of episodic imagery (Peters & Buchel, 2010). Additionally, participants may record their highest rated events into audio cues.

Experimenters will train participants in the EFT group on how to retrieve cues from their cell phone or alternative internet accessible device (e.g. laptop, tablet, desktop computer), to pay attention to and think about the cues, and how to adhere to the study's expectations for utilizing the cues. If participants do not have an internet accessible device one may be provided to them (e.g. smartphone) for the duration of the study at no cost to them. Participants may be prompted several times a day to use their cues and instructed to use their cues any time that need to, especially around eating episodes, using the thought training website – Mobile Audio Management and Response Tracker (MAMRT) (Sze, Daniel, Kilanowski, Collins, Epstein, 2015).

Ecological momentary intervention (EMI) uses mobile technology to deliver interventions to individuals during their everyday lives (i.e. in real time) and in their natural settings (i.e. real world). EMIs enhance the ability to influence behavior in real-world contexts as participants often experience tempting food situations in their natural environments. In this study, the EMI will involve daily prompts to use EFT cues and answer questions about their cues using the thought training (MAMRT) (Sze, Daniel, Kilanowski, Collins, Epstein, 2015). MAMRT will deliver cues/prompts daily to participants. Participants will also be able to access MAMRT and their EFT cues as many times a day as they desire.

During individual sessions case managers may review progress, habit changes, medication adherence, and use of EFT. In the control group participants will not use cues but will still be prompted to log into the MAMRT website and answer questions about their eating behaviors. Participants in the control group will otherwise engage in the same tasks. During weeks when participants do not visit the lab and do not meet with their case manager, they may be contacted by phone, email, or text by their case manager to check in and review progress, similar to an in-person case management meeting.

In response to the coronavirus pandemic, we are enacting preventative measures to ensure both participants and employees limit exposure. For group sessions and case management sessions, this may entail conducting group sessions by sending

participants a recorded video or using a password-protected video conference (Such as via Webex or Zoom Meeting) on a secured network. In this event, a link with a password to access the secured meeting room would be sent to participants and necessary staff. Case management sessions intended to occur in-person may also be carried out via secured video conference or by phone. As is the case for in-person group sessions, video-conference group sessions may be audio or video recorded so that if a participant misses the meeting, they are able to receive the information and learn the materials on their own time.

The impact of the coronavirus on participants will be monitored via a questionnaire to be administered about once a month. The questionnaire may ask about any major changes participants have experienced, a measure of delay discounting, questions about food demand, perceived stress, loneliness as well as perceived risk of testing positive for coronavirus. This may be administered via phone/video conference interview or via survey link sent to participants. The MAMRT website will be used to provide information about the intervention, downloadable manuals for the Traffic Light Diet and Activity Program, provide tools for cooking and getting more physical activity, and managing the EFT component of the intervention where participants may be able to read and listen to recordings of their self-generated EFT cues. Quizzes to assess mastery of educational materials will be implemented on the study website, with multiple versions of quizzes on each module available to account for those participants who will acquire the information more slowly than others. . Participants may have access to traditional paper and pencil self-monitoring. After self-monitoring skill is acquired, participants can choose to use traditional or technology-based recording. The website will also contain password protected sections that are for internal use by study personnel. The website will not contain protected health information.

Participants will also be taught how to record food and drink, exercise, and at home weight measurements in MyFitnessPal. MyFitnessPal is a smartphone and web based app that tracks diet and exercise and can record the number of calories, macro and micronutrients consumed. These recordings may be shared with their case manager and other study team members to review progress and behavior change.

Measurements for blood HbA1c, blood pressure, cholesterol, height and weight measured to calculate BMI, measures of delay discounting, food demand, other executive functions (e.g. working memory), energy intake, physical activity, and medication adherence will be collected at baseline, 3 months, and 6 months. In response to the coronavirus mandatory closures, these assessment measures may also be recorded remotely. In the event that a participant must have assessment measures performed remotely, a staff member may conduct a conference call or video conference with the participant to instruct them on how to complete questionnaires and complete executive function tasks online via online survey (For example, on Qualtrics). The staff member may also instruct the participant on how to weigh themselves and observe the participant taking their weight at home via video conference. In order to collect A1c measures for remote

assessment sessions, participants may be sent an A1CNow test kit (PTS Diagnostics, *Sunnyvale, CA*), a commonly used self-administered A1c test that is available over-the-counter and that provides a valid measure of A1c (Chang et al., 2010), and may also be observed conducting the at-home A1c test by a staff member. In addition, participants may be sent an Actigraph with instructions on its use in order to assess physical activity for remote assessments. At the 3 and 6 month assessment sessions, an adverse event questionnaire will also be administered. After completion of the final assessment session, study staff will request records of participants' prescription refills from their current pharmacies and will be debriefed about the study. Participants may also be asked if they would be willing to anonymously complete a study evaluation on which participants can check a box to indicate whether or not they would allow their anonymous responses to be shared with others as testimonials. Research staff will be able to answer any questions the participant may have about the group they were assigned to at that time. For those consenting to be recontacted for a longer-term follow up, there may be an additional assessment at the 12-month time point that will entail follow-up measures of A1c, delay discounting and weight and could be conducted via video conferencing in the same manner as assessments done during the coronavirus mandatory closures. In addition, participants electing to complete the 12-month assessment will also complete the coronavirus and AE questionnaires.

Week #	Screening	0 (base line)	Month 1				Month 2				Month 3		Month 4	Mont h 5	Month 6	Month 12***
			1	2	3	4	5	6	7	8	9-10	11-12	13-16	17-20	21-25	~52 weeks
Group Meeting Topic*		Orien tation	TLD	TLD	Meal Planni ng	Phys ical Acti vity	Portion Contro l	EFT/C ontrol	High Risk Situatio ns	Stimulu s Control	Review, Portion Control	Shoppin g Healthy **	Self- monitorin g weight	EFT/RT in high risk situation s	Maintaini ng Healthy Habits**	
Review with Case Manager			X	X	X	X	X	X	X	X	X	X	X	X	X	
Primary Assessment Session		X										X			X	X
DD Assessment with EFT Cues									X				X		X	X
Wearing Actigraph		X										X			X	
Use Cues On MAMRT									Starts around week 7							
Compensatio n		X										X			X	X

*Group meeting topics are subject to change and may be presented in a different order.

**Group meeting content may be shared via video in lieu of in-lab group session.

*TLD = Traffic Light Diet

*** 12-month session only for those consenting to re-contact following 6-month assessment – to be conducted via video conferencing

12.0 Measurements

Recordings: Sessions where treatment is delivered may be audio or video recorded for Clinical Supervisor to review treatment fidelity and provide feedback to Interventionists/Case Managers.

Demographics and Health Behavior: Race/ethnicity, household income, and educational level will be assessed using a survey-based questionnaire. Participants will also be asked about their health behavior, including substance use, mental health, medical history, and food consumption.

Food Consumption Questionnaire. Food consumption, including any food or beverages ingested in the last 24 hours will be measured using the ASA24 (Automated Self-Administered Recall System).

Major Life Events: Individuals will be asked to complete the major life events questionnaire which measures major life events that may have been experienced during their involvement in the study. Individuals who are undergoing major life events such as a move, new baby or a new job may influence their performance on study measures and tasks.

Financial Planning and Longevity. Individual differences in time period of financial planning will be assessed with the question, “In planning your, or your family’s, saving and spending, which of the time periods is more important to you and your partner, if you have one?” (Picone, Sloan, & Taylor, 2004). Answer choices provided will range from not planning, to planning longer than ten years. Financial planning will be reported categorically, and will be converted to a continuous variable for analysis using midpoints of the categories. Subjective probability of living to age 75 will be measured by asking “What do you think are the chances you will live to be 75 or more (where 0 means there is no chance you will live to 75 or more, and 100 means you will definitely live to 75 or more)” (Picone et al., 2004). Higher values on either question will indicate greater future orientation.

Time Perspective: Individual differences in temporal perspective will be assessed using measures that assess temporal orientation. Consideration of Future Consequences Scale (CFCS). CFCS assesses the extent to which individuals consider the potential future outcomes of their current behavior and the extent to which they are influenced by the imagined outcomes (Strathman et al., 1994).

Positive and Negative Affect Schedule (PANAS): The PANAS comprises two mood scales, one that measures positive affect and the other which measures negative affect (Watson et. al., 1988).

Medication Adherence (pill counts): Participants will be asked to bring their prescription bottles to both baseline and follow-up visits. Remaining pills will be counted and medication adherence will be calculated as: $(\text{quantity dispensed} - \text{remaining}) / (\text{quantity prescribed per day} * \text{days since last refill}) * 100$, yielding a measure of percent adherence. In addition, we will utilize participant refill history from their pharmacies to estimate prescription adherence from baseline to final assessment.

Medication Adherence (self-report): Participants will complete a self-report medication adherence questionnaire validated for use with patients with type 2 diabetes, yielding a measure of percent adherence.

Height, Weight, BMI: Participants' height will be assessed using a digital stadiometer. Participants' weight will be assessed using a digital scale. Based on the height and weight data, Body Mass Index (BMI) will be calculated according to the following formula: $BMI = \frac{kg}{m^2}$. These are the current standards set forth by the Centers for Disease Control and Prevention (Kuczmarski et al., 2002).

Blood pressure: Blood pressure will be measured 3 times using an OMRON automated blood pressure device by trained personnel. The latter two readings will be averaged.

Hemoglobin A1c (HbA1c): HbA1c will be measured using the A1CNow+® or A1CNow® self-check systems (PTS Diagnostics, Sunnyvale, CA) or the Alere Afinion™ AS100 Analyzer System (Abbott, Abbott Park, IL).

Blood Glucose: Blood glucose may be measured using the FreeStyle Lite Glucose Monitor or the FreeStyle Libre Pro (Abbott, Abbott Park, IL).

Cholesterol: Blood for lipid profile (e.g., total cholesterol, HDL, LDL, triglycerides, HDL/LDL ratio, etc.) will be measured using the Alere Cholestech LDX® system (Alere Inc., Coral Springs, FL).

Physical Activity: Physical activity may be measured using the Actigraph WGT3X-BT accelerometer. Participants will be shown how to properly wear the monitors and will be asked to wear their monitors for about a week. Data will be collected at a rate of 30 Hz and converted to one minute epochs for data analysis. Total activity counts and activity in the moderate to vigorous (MVPA) and vigorous (VPA) ranges will be estimated. Physical activity may be measured using a Fitbit (San Francisco, CA) or other activity monitor.

Subjective Hunger: Participants will be asked to provide subjective ratings of their hunger. Hunger will be assessed using a 5-point Likert scale (anchored by 1-Extremely Full and 5-Extremely Hungry).

Subjective Preferences: Participants may be asked to provide subjective ratings of their food/activity preferences by ranking, rating their liking using a 5-point Likert scale (anchored by 1-Do not like and 5-Like very much), and making choices between their food/activity.

Cue Attention: A Likert-style scale assessing attentiveness to the episodic cues and vividness cues during tasks will be assessed on a scale from 1 to 5, where 1 indicates "not at all" and 5 indicates "very much".

Delay Discounting: An operational definition of impulsivity is delay discounting, the degree to which a person will discount the value of a larger delayed reward in favor of a smaller immediate reward. Computerized/ experimenter administered assessments will provide participants with choices between a smaller amount of a hypothetical commodity available immediately or a larger amount available later. Participants will make choices between rewards such as money, food, physical activity, and health gains. Two methods may be used to measure discounting, Adjusting Amount and Adjusting Delay.

Adjusting Amount Discounting. The magnitude of the immediate commodity is adjusted until it is subjectively equivalent to the later larger amount. Subjective equivalence will be obtained at delays such as; 1 day, 1 week, 1 month, 3 months, 6 months, and 1 year. To ensure comparison between money and non-monetary rewards, prior to running the discounting programs for food, physical activity and health, participants will indicate the amount of the commodity whose receipt “right now” would be equally valuable to the participants as receiving a set amount of money, for example \$100. Participants may be presented with their EFT cues before making decisions at each delay period.

Adjusting Delay Discounting. The adjusting delay discounting task is a five trial task in which participants are asked how much money they would prefer (e.g. \$500) immediately or a larger reward after a delay (e.g. \$1000). This task is presented on a computer screen and is designed to measure the amount of monetary discounting that occurs when rewards are presented at a delay. This task adjusts the delay to the larger reward and allows for the calculation of k-values. This task will be completed matching each of the traditional tasks parameters (i.e. type and magnitude of the reinforcer).

Executive Function: Cognitive processes, such as planning, cognitive flexibility, working memory, prospective memory, retrospective memory and attention may be measured by using computerized tasks or paper and pencil that involves solving problems, remembering a set of letters or spatial locations while alternating with a distracter tasks (e.g., Backwards CORSI).

Relative Reinforcing Efficacy Food Purchasing Task: The food purchasing task is modified off of the cigarette purchasing task (CPT) that has been used by Jacobs and Bickel (1999) and assesses a number of different metrics of relative reinforcing efficacy. The procedure we will use is a modified version of this procedure and will assess the relative reinforcing efficacy of a range of foods via an online survey or computerized task. The chosen food will be displayed during the task so that participants have a frame of reference when completing the questionnaire.

Coronavirus Questionnaire: A questionnaire developed to monitor the effects of the coronavirus pandemic on participants will include a modified Major Life Events questionnaire similar to that described above but asking about a longer time frame (about a month), the five-trial Adjusting Delay Discounting task described above, food purchasing questions asking the maximum amount a participant would spend on preferred snack foods, a question asking if participants know someone diagnosed with coronavirus, a question asking their perceived risk of being diagnosed with coronavirus (measured on a 0-100 scale), two self-report questionnaires the 10-item Perceived Stress Scale (PSS; Cohen, 1994), and the 5-item Loneliness Scale from the NIH toolbox for assessment of neurological and behavioral function (Gerson et al., 2013). The PSS asks that participants rate on a 5-point scale (0 = never; 1 = almost never; 2 = sometimes; 3 = fairly often; 4 = very often) how often over the last month they have thought or felt different situations were stressful. Example questions include, “In the last month, how

often have you been upset because of something that happened unexpectedly?" and, "In the last month, how often have you felt that things were going your way?" The 5-item longlines scale asks participants to select how often over the past month they feel lonely as described by 5 different statements. Answers are given on a 5-point Likert scale (1 = Never; 2 = Rarely; 3 = Sometimes; 4 = Usually; 5 = Always). Example statements include, "I feel alone and apart from others" and "I feel that I am no longer close to anyone".

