At the in person session 1 screening appointment, all participants will be given the Eating Disorder Examination (EDE) Questionnaire which is a well-established

and valid measure for eating disorders (J.M Mond et. al. 2004). If it is determined that they may have an eating disorder other than binge-eating disorder, the participant will not be eligible to continue with the study, and their physician may be notified. Binge-eating disorder or binge-eating disorder symptomology will not be considered exclusionary as behavioral weight loss treatment is both safe and effective for individuals with binge-eating disorder and binge-eating disorder symptomology (Grilo et al., 2011; Munsch et al., 2007). All participants who complete the EDE will be provided with a list of resources.

At the in person screening visit (session 1) documented consent will be obtained from potential participants. During the screening procedure, participants will be asked to sign a medical release form allowing the primary care physician to provide us with the information regarding eligibility and also allow us to send any pertinent medical information to their primary care physician (i.e. diagnoses of obesity, prediabetes, hypertension, dyslipidemia, depression score assessed by the BDI). If we do not receive the form within about 5 business days we will call to follow up with the primary care physician. Participants will also be asked to sign a release form for relevant pharmaceutical records (e.g. refill history of medications used to treat pre-diabetes, diabetes, and/or hyperlipidemia and hypertension) from their current pharmacy. Release of pharmaceutical records may be attained through the end of study participation if not attained at screening and will cover the period from about 90 days prior to screening to about the end of study participation. At the screening visit, participants will have their HbA1c levels measured by finger stick to obtain a drop of blood. If subjects meet eligibility criterion based on HbA1c levels (approximately 5.4% - 6.7%) at the initial screening visit, they may be eligible to participate regardless of confirmatory PCP diagnosis. Additionally, participants will be assessed for hyperlipidemia by finger stick and blood testing as well as for hypertension using an automated blood pressure machine.

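### The pill-count adherence formula omits pills on hand at the last refill and ignores all time before it, so the score depends on refill timing

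*Combined protocol and SAP*

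**What the plan says.** Section 12.0 (Medication Adherence, pill counts) plans the count at several visits: "Participants will be asked to bring their prescription bottles to both baseline and follow-up visits". Section 11.0 gives the times: "medication adherence will be collected at baseline, 3 months, and 6 months".

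The score is a closed formula, introduced by the words "Remaining pills will be counted and medication adherence will be calculated as". Its numerator is "quantity dispensed" less the pills remaining. Its denominator is "quantity prescribed per day" multiplied by "days since last refill". The ratio is expressed as a percentage. No rule is given for pills left from an earlier fill, for which bottles are counted, or for values outside 0 to 100%.

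Section 12.0 adds two further measures. One is a pharmacy measure: "we will utilize participant refill history from their pharmacies to estimate prescription adherence from baseline to final assessment". The other is a self-report questionnaire that also yields a percentage. Under Section 9.0 the pharmacy release "will cover the period from about 90 days prior to screening to about the end of study participation". The refill measure has no formula, and no section says which of the three measures is the outcome for Secondary Aim 1 or how they combine.

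**The concern.** The numerator credits only the latest fill, and the clock starts at that fill. Two consequences follow.

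- **Carry-over.** Pills left when the new supply arrives are later counted as remaining, or are taken in place of new ones, but never enter the supply. Someone who refills before running out looks as if doses were missed.
- **Gaps.** Days without medication before the latest refill fall outside the window, so they cost nothing.

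The formula can therefore rank a participant with a real interruption above one who missed nothing. Secondary Aim 1 (Section 2.0) compares the arms on change in adherence to hypertension and hyperlipidemia medication over 6 months. A change score would carry this error at both ends. Exploratory Aim 1 also uses improvement in medication adherence as an outcome.

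**Working it through.** **Inputs.** The formula is from Section 12.0. Write D for the quantity in the latest fill, R for pills remaining, q for pills prescribed per day, d for days since that fill, and C for pills on hand when it was collected. The documents give no values for D, q, d or C. The examples assume q = 1 and D = 30 unless stated. There is no figure in the plan to reproduce.

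**Stated formula.** Score = 100 × (D − R)/(q × d).

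**1. Carry-over, no dose missed.** If all pills on hand are counted, R = D + C − qd. Substituting:

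score = 100 × (qd − C)/(qd) = 100 × (1 − C/(qd)).

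D cancels, so a 90-pill fill gives the same values on the same day. The true value is 100% in every cell.

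| C | day 10 | day 20 | day 30 |
|---|---|---|---|
| 2 | 80% | 90% | 93.3% |
| 5 | 50% | 75% | 83.3% |
| 10 | 0% | 50% | 66.7% |

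For example, with C = 5 at day 10, R = 30 + 5 − 10 = 25 and (30 − 25)/10 = 50%. With 10 pills carried over and a 90-pill fill counted at day 60, the score is 100 × (1 − 10/60) = 83.3%.

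**2. Dependence on the counting convention.**

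| C = 5, D = 30 | R at day 3 | score | R at day 10 | score |
|---|---|---|---|---|
| all bottles pooled | 32 | −67% | 25 | 50% |
| new bottle only, old pills used first | 30 | 0% | 25 | 50% |
| new bottle only, new pills used first | 27 | 100% | 20 | 100% |

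Negative scores need pooled bottles and a count soon after the refill. The carry-over error disappears only under the third convention, which the protocol does not state.

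**3. Gap that ended before the count.** Thirty pills are taken in 30 days, 15 days pass without pills, a refill is collected, and all 10 doses since then are taken. R = 20, so the score is (30 − 20)/10 = 100%. From the start of the earlier fill, 40 doses were taken over 30 + 15 + 10 = 55 days, or 40/55 = 73%. With gaps of 10, 20, 30 and 60 days the score stays at 100%, while the true values are 40/50 = 80.0%, 40/60 = 66.7%, 40/70 = 57.1% and 40/100 = 40.0%.

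**4. Gap still open at the count.** Here the formula does respond. Thirty pills used and no refill gives 30/40 = 75% at day 40 and 30/60 = 50% at day 60.

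**5. Between-visit balance on the same cases.** Suppose the previous visit fell on the day of the earlier fill, with 30 pills on hand.

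- Carry-over case: the refill comes at day 25 with 5 pills left and the count at day 35, so (30 + 30 − 25)/35 = 100%.
- Gap case: the count comes at day 55, so (30 + 30 − 20)/55 = 73%.

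Both match the truth.

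**The case against.** - **The pill count is not the only objective measure.** A reader might infer that Secondary Aim 1 rests on it. The documents do not support that: refill history from baseline to the final assessment is a second objective source and can show gaps before a refill, and self-report is a third. This stands. Neither source corrects the pill-count percentage, however, and the three are not ranked.
- **The direction of bias is unknown.** One might argue that earlier refilling under BT-EFT would depress that arm's scores. Nothing in the documents gives refill timing, carry-over or gap frequency by arm. Without such a difference, randomization balances carry-over in expectation and the problem is mainly noise. This stands.
- **Running out of pills is not always hidden.** It is hidden only if the gap ended with a refill before the count (step 4). This stands.
- **The size varies.** The 50% figure is illustrative. The error shrinks as days since the refill grow and depends on which bottle is counted and used first. This stands, but no counting rule is written, and the gap problem remains under any convention.
- **The reach is limited.** The measure applies only to participants taking the relevant medication. The primary endpoints and the sample size are untouched, and Section 14.0 does not name medication adherence among the outcomes to be analyzed. This limits the consequences but does not make the formula correct.

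**Conclusion.** The concern holds as a measurement error. As written, the formula gives wrong values for identifiable and ordinary refill patterns. At one pill a day, with all pills counted or old pills used first, a fully adherent participant carrying over 5 pills scores 50% at day 10 and 83% at day 30. If bottles are pooled, the score can be negative soon after a refill. A participant whose 15-day gap ended before the count scores 100% against 73%.

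The effect is error tied to refill timing in one of three measures for a secondary aim. How often these patterns occur cannot be estimated from the documents, and a bias between arms is not shown. The point should be corrected, but it does not affect the primary comparisons.

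**What to change.** At 3 and 6 months, replace the formula with a between-visit balance that counts all bottles:

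100 × (pills on hand at the previous visit + all pills dispensed between the visits per pharmacy record − pills on hand now) / (pills prescribed per day × days between the visits).

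Compare the arms on this follow-up value. There is no earlier planned count from which to form the balance at baseline, so use adherence from the pharmacy record for about 90 days before screening as a covariate only. If a change score is wanted, compute it from refill history at both times. Do not subtract a pharmacy-based baseline from a pill-balance follow-up: one measures possession and the other pills used.

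The cost is a short text change, since the counts and records are already planned. Three practical limits apply:

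- Under Section 11.0, pharmacy records are requested after the final assessment, so the 3-month value would be computed retrospectively.
- Section 9.0 allows the release to be obtained as late as the end of participation and refers to the current pharmacy, so some records may be missing or incomplete.
- Remote assessments under Section 11.0 may leave a count incomplete.

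Participants without released records or a complete previous count therefore need a fallback. One option is the current formula with pills on hand at the refill added to the numerator where known; in the day-10 example this gives (30 + 5 − 25)/10 = 100%. It still misses gaps before the refill, so these participants should be flagged and examined in a sensitivity analysis.
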